13.2 Informed Consent

The investigator (or his/her designee) will explain to each subject the nature of the study, its purpose, the procedures involved, the expected duration, the potential risks and benefits involved and any discomfort it may entail. Each subject will be informed that participation in the study is voluntary, that she may withdraw from the study at any time, and that withdrawal of consent will not affect her subsequent medical treatment or relationship with the treating physician(s) or institution. The informed consent will be given by means of a standard written statement, written in non-technical language, which will be IRB approved. The subject should read and consider the statement before signing and dating it, and will be given a copy of the document. No subject will enter the study or have study-specific procedures done before his/her informed consent has been obtained.

In accordance with the Health Information Portability and Accountability Act (HIPAA), the written informed consent document (or a separate document to be given in conjunction with the consent document) will include a subject authorization to release medical information to the study sponsor and supporting agencies and/or allow these bodies, a regulatory authority, or Institutional Review Board access to subjects' medical information that includes all hospital records relevant to the study, including subjects' medical history.

13.3 Ethics and GCP

This study will be carried out in compliance with the protocol and Good Clinical Practice, as described in:

1. ICH Harmonized Tripartite Guidelines for Good Clinical Practice 1996.
2. US 21 Code of Federal Regulations dealing with clinical studies (including parts 50 and 56 concerning informed consent and IRB regulations).
3. Declaration of Helsinki, concerning medical research in humans (Recommendations Guiding Physicians in Biomedical Research Involving Human Subjects, Helsinki 1964, amended Tokyo 1975, Venice 1983, Hong Kong 1989, Somerset West 1996).

The investigator agrees to adhere to the instructions and procedures described in it and thereby to adhere to the principles of Good Clinical Practice that it conforms to.

14. STATISTICAL CONSIDERATIONS

14.1 Endpoints

14.1.1 Study Design

This is a multi-institutional, randomized, two-arm, phase II trial of endorectal brachytherapy alone (Endo-HDR) versus intensity modulated external beam radiotherapy (IMRT) or 3-D conformal radiation therapy with capecitabine in patients with stage II/III rectal distal adenocarcinoma. Patients enrolled in the study will be randomized (2:1 ratio) to either Endo-HDR or standard external beam chemoradiation.

14.2 Sample Size/Accrual Rate

14.2.1 Sample Size and Power

We will screen a total of 165 patients for the trial. Based on our phase II single arm endorectal brachytherapy study, we expect approximately 20% of candidates will drop out because of unexpected findings on PET/CT (i.e. metastases) or MRI (i.e. iliac/inguinal lymph nodes). Therefore, we expect to randomize 138 patients in 2:1 ratio into two treatment arms (92 in the Endo-HDR arm and 46 in the control arm). Using a one-sided Fisher's exact test at significance level 0.1, we will have 80% power to detect a 17% increase of pathologic complete response rate from the 13% in the control treatment arm to 30% pCR in the Endo-HDR arm. After randomization, we expect <5% drop-out rate.

One interim analysis for early assessment of futility is planned after 69 patients (half of the total planned sample size) have had their pCR evaluation. The trial will be terminated early if the ratio of the pCR rate in the Endo-HDR arm vs. control arm is 1 or less, i.e., the Endo-HDR treatment appears the same or worse than the control treatment by any amount. This leads to minimal loss of power compared to an analysis without intermediate look.

14.2.2 Accrual Rate

Each center will enroll approximately 1 patient per month or 10-12 patients per year per site or approximately 60 patients total per year with six centers. With the appeal of a shorter treatment course and potential for decreased toxicity from radiotherapy, we are confident that we will accrue actively to meet our target goals. However, if we do not enroll 30 patients after 6 months, we will add additional sites.

14.3 Early Stopping Guidelines

One interim analysis for early assessment of futility is planned after 69 patients (half of the total planned sample size) have had their pCR evaluation. The trial will be terminated early if the pCR rate in the Endo-HDR arm is less than the control group (standard chemoradiation). If the pCR rate is the same or better with endorectal brachytherapy, the trial will continue. This leads to minimal loss of power compared to an analysis without an intermediate look.

14.4 Analysis of Primary Endpoint

The primary endpoint is pathologic complete response rate, which will be estimated for both arms as the proportion of patients who achieve pathologic complete response after the treatment. The corresponding 95% confidence intervals will be calculated. The comparison of pCR between the two arms will be performed using Chi-square test. The primary analysis of the pCR endpoint will be based on the intent-to-treat population which includes all randomized patients where patients are classified according to the randomized treatment assignment regardless of what treatment was received.

14.5 Analysis of Secondary Endpoints

Secondary endpoints of this phase II trial include toxicity, quality of life, locoregional control/distant metastasis, overall survival, and correlative analyses of biomarkers and functional imaging changes.

The acute and chronic toxicity and adverse events will be summarized in frequency tables by type and grade for each arm and will be compared between arms using Fisher's exact tests.

Quality of life will be assessed via EORTC QLQ-C30 (v3.0) questionnaires as mentioned above. Scoring will be based on procedures outlined by the EORTC. For our study population of rectal cancer patients, the analysis will be focused on general and colorectal model regarding urinary/bowel toxicity, sphincter function, and sexual dysfunction. For each module, summary statistics of the scores will be reported at baseline and each follow-up time. After confirming that there are no baseline differences in quality of life across the two treatment arms using independent samples t-test, changes in quality of life scores from pre- to post-treatment will be computed, and the difference between these change scores will be evaluated by paired-sample t-tests. We will compare the quality of life scores at each endpoint as well as the differences between the two arms using two-sample t-test. Given the plurality of comparisons, p-values <0.01 will be considered statistically significant. In addition, mixed effect models will be used for assessing the quality of life change over time and comparing the two treatment arms. For instance, mixed effects models will be used to assess changes in QOL over time first in all study patients and then to compare the effects of the two treatment arms on change in QOL over time. Need for sexual aids will be compared in a descriptive fashion between the two cohorts.

Overall survival, distant metastases free survival, progression free survival, and local recurrence will be measured from the date of randomization to the date of death due to any causes. Patients last known to be alive are censored at date of last contact. Kaplan-Meier curves will be used to characterize overall survival in each arm and log rank test will be used for the comparison.

The analysis of correlative endpoints of imaging and biomarkers will be exploratory.

For all patients in both study arms, the presence of VEGF/EGFR status will be assessed using pre-treatment tumor biopsies prior to the start of radiation therapy. The result will be expressed as a binary variable indicating the presence of expression (positive/negative). Its association with pCR will be assessed using Fisher's exact test. We will also examine the role of VEGF/EGFR and other hypoxia related biomarkers as a predictive marker for tumor response following Endo-HDR treatment by testing the interaction of the treatment group and VEGF/EGFR status using a logistic regression model where pCR is the dependent variable.

For those treated with Endo-HDR, we anticipate the pCR rate to be 40% among patients with favorable VEGF/EGFR and/or hypoxia marker signature compared to 10% pCR in the group with unfavorable signature. If we observe 40% patients with unfavorable profile, with 92 patients in the Endo-HDR arm, the test will have 89% power.

Prevalence of unfavorable signatures	Power
^a	
^b 25%	0.77
^c 40%	0.89
^e 50%	0.90
^d 75%	0.85

Table 3. Power to detect a 30% difference under various observed prevalence of unfavorable VEGF/EGFR and/or hypoxia marker signatures using a two-sided Fisher's exact test at significance level 0.05.

To assess the correlation of functional PET/MR and treatment response, we will compare the change of SUV pre- and post-treatment between responders and non-responders using a two-sample t-test. Non-parametric Wilcoxon test will be considered when the data are not normally distributed. For a binary response outcome, the predictive ability of the PET/MR marker will be evaluated using an ROC curve based on a logistic regression model in which the imaging marker will be entered as an independent variable.

REFERENCES:

1. Prolongation of the disease-free interval in surgically treated rectal carcinoma. gastrointestinal tumor study group. *N Engl J Med.* 1985 Jun 6; 312(23): 1465-1472.

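### Section 14.5 assigns a paired-sample t-test to the difference between QOL change scores, which that test cannot compare between independent arms and which conflicts with the valid between-arm methods named next

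*Combined protocol and SAP*

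**What the plan says.** The QOL paragraph of section 14.5 (Analysis of Secondary Endpoints) runs in this order.

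- It opens with a between-arm baseline check: "After confirming that there are no baseline differences in quality of life across the two treatment arms using independent samples t-test".
- The same sentence then sets up the change scores: "changes in quality of life scores from pre- to post-treatment will be computed".
- It closes by naming the test at issue here: "the difference between these change scores will be evaluated by paired-sample t-tests".
- The next sentence reads: "We will compare the quality of life scores at each endpoint as well as the differences between the two arms using two-sample t-test".
- The significance rule for these comparisons is that "p-values <0.01 will be considered statistically significant". It does not say whether the tests are one- or two-sided.
- Mixed effects models follow, first for all patients and "then to compare the effects of the two treatment arms on change in QOL over time".

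The arm sizes come from section 14.2.1: "92 in the Endo-HDR arm and 46 in the control arm". Patients are randomized 2:1 (section 6.5), and the secondary objective in section 4.2 is to compare QOL between Endo-HDR and chemoradiation.

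**The concern.** The sentence that names the paired test begins with the two arms and then speaks of a difference between change scores. Read in that frame, it is a contrast between Endo-HDR and control. A paired-sample t-test cannot make that contrast, because the scores come from different patients and nothing links a patient in one arm to a patient in the other.

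If the authors meant a pre/post test inside each arm, the test is valid, but it tests whether mean change differs from zero. That is not a difference between change scores, and it does not answer the objective in section 4.2. Under either reading the sentence does not describe a workable analysis of what it names, and it sits beside a sentence that gives a different test for the differences between arms.

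What is at stake is the clarity of the QOL report. An analyst following the text could produce within-arm p-values and present them as the evaluation of the change-score difference. A reader could then take significance in one arm only as a treatment effect.

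**Working it through.** **1. The plan's own figure.** The documents give no power or sample size for QOL. The figure behind the arm sizes is the power statement for pathologic complete response in section 14.2.1: "Using a one-sided Fisher's exact test at significance level 0.1, we will have 80% power", for 13% against 30%. Exact enumeration of the one-sided Fisher test with 46 control and 92 Endo-HDR patients gives 0.802. The figure reproduces, so 92 and 46 are used below.

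**2. Can the named test be run between arms?** A paired t-test forms D_i = X_i − Y_i for each linked pair i and uses t = mean(D) / (s_D/√n). It needs the same number of X and Y values and a link between them. Here there are 92 and 46 values from different patients, so the test is undefined.

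**3. What does it test within an arm?** With X the post-treatment and Y the pre-treatment score of one patient, it is a one-sample t-test that mean change equals zero. No term for the other arm enters.

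**4. Illustration: what if the two within-arm results were set against each other?** The plan does not call for this. Assumptions: two-sided 0.01, complete data, normal changes with equal SD, and the same true standardized change d in both arms. The documents supply no QOL SD or effect size, so d is an assumed range.

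Within-arm power is P(|T| > t(0.995, n−1)), with T noncentral t on n−1 degrees of freedom and noncentrality d√n. The critical values are 2.631 (n = 92) and 2.690 (n = 46). At d = 0.3 the noncentralities are 0.3√92 = 2.877 and 0.3√46 = 2.035, and the powers are 0.598 and 0.269.

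P(exactly one arm significant) = p92(1 − p46) + p46(1 − p92). At d = 0.3 this is 0.598 × 0.731 + 0.269 × 0.402 = 0.437 + 0.108 = 0.545.

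The last column is the same quantity for two equal arms of 138/2 = 69.

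| d (SD) | Power, n = 92 | Power, n = 46 | Endo-HDR only | Control only | Exactly one | Exactly one, 69/69 |
|---|---|---|---|---|---|---|
| 0 | 0.010 | 0.010 | 0.010 | 0.010 | 0.020 | 0.020 |
| 0.1 | 0.051 | 0.028 | 0.050 | 0.026 | 0.076 | 0.075 |
| 0.2 | 0.244 | 0.102 | 0.219 | 0.077 | 0.297 | 0.282 |
| 0.3 | 0.598 | 0.269 | 0.437 | 0.108 | 0.545 | 0.493 |
| 0.35 | 0.764 | 0.386 | 0.469 | 0.091 | 0.560 | 0.479 |
| 0.4 | 0.883 | 0.515 | 0.428 | 0.060 | 0.489 | 0.378 |
| 0.5 | 0.983 | 0.755 | 0.241 | 0.012 | 0.254 | 0.130 |
| 0.6 | 0.999 | 0.910 | 0.090 | 0.001 | 0.091 | 0.022 |
| 0.7 | 1.000 | 0.977 | 0.023 | 0.000 | 0.023 | 0.002 |

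The curve peaks at about 0.57 near d = 0.33. Simulation (40,000 runs) agrees: Endo-HDR only 0.439 and control only 0.105 at d = 0.3; 0.426 and 0.062 at d = 0.4.

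**5. The between-arm test already in the plan.** Under the same conditions, the two-sample t-test on change scores has a false-positive rate of 0.010 whatever the common change (simulated: 0.0101 at d = 0.3, 0.0106 at d = 0.4).

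**The case against.** The strongest reply is that the paragraph already contains a valid arm comparison. Its next sentence gives a two-sample t-test for the differences between arms, and the mixed models compare the arms on change over time. The authors also use unpaired tests for both explicit arm comparisons, so they evidently know the distinction, and the paired test may have been meant for something else. One candidate is pre/post change within patients. Another is a comparison of one patient's changes at different visits: section 9.1 schedules the EORTC questionnaires at baseline, pre-op, post-op and years 1 to 5, so each patient has several change scores that could properly be paired.

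Much of this stands. It rules out the inference that the trial has no valid between-arm QOL analysis. It does not rescue the sentence. Neither alternative is written down, the text speaks of a single pre-to-post-treatment change in a sentence about the two arms, and neither alternative compares arms.

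A reader might also infer that the within-arm tests would turn the unequal arm sizes into an apparent treatment effect. The documents do not support that. A within-arm paired test is valid for within-arm change, and a false arm effect needs the further step of comparing the two p-values, which no section plans. Nor is allocation the main cause: equal arms would disagree in 49% of trials at 0.3 SD and 48% at 0.35 SD, against 55% and 56% for 92 and 46.

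**Conclusion.** The point holds as a mis-specified test on a secondary endpoint. As a contrast between arms the paired test cannot be run; as a within-arm test it does not evaluate a difference between change scores; and it conflicts with the between-arm methods in the following sentences. Pathologic complete response, the sample size and the interim rule are unaffected.

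The percentages show why within-arm p-values should not stand in for an arm comparison. They do not forecast an error in this trial. They run from 2% to about 57% over an assumed 0 to 0.7 SD, and they rest on an identical true change in both arms, a two-sided 0.01 level, no missing QOL data and normal changes with equal SD. What 2:1 allocation mainly adds is direction: at 0.35 SD, significance in Endo-HDR only is about five times as likely as in control only (0.469/0.091), whereas equal arms would split evenly.

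**What to change.** In section 14.5, remove the paired-sample t-test as the test of the difference between change scores. State that QOL change is compared between arms only by the two-sample comparison or the mixed-model arm-by-time contrast already planned there; if both are kept, say which one carries the conclusion.

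If paired pre/post results are wanted, report them per arm as mean change with a confidence interval, labelled descriptive, and state that no between-arm conclusion will be drawn from one arm being significant and the other not.

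The cost is an edit of about a sentence, with no new data and no added analysis.

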4.2 Secondary Objectives

- Test whether clinical response based on functional imaging (PET, MRI) pre/post radiation (Endo-HDR vs. CRT) predicts for pathologic complete response.
- Utilize preoperative imaging response rates and clinical exam to determine whether Endo-HDR results in improved sphincter preservation rates when compared to CRT.
- Determine whether tumor (VEGF/EGFR status) and blood predict for pathologic response following neoadjuvant Endo-HDR vs. CRT.
- Compare acute and long-term toxicity as well as quality of life for both Endo-HDR and CRT.
- Compare locoregional control, distant metastasis and overall survival for both Endo-HDR and CRT.

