6.5 Randomization

Eligible subjects will be randomly assigned in a 2:1 ratio to receive either endorectal brachytherapy or IMRT using the method of randomly permuted blocks in strata defined by study site. The patient may be enrolled and randomized before the endoscopic ultrasound and fiducial placement if all eleigibility requirements are met. A master list of randomization assignments will be made by the protocol statistician, and will be delivered to the lead site by email or facsimile report.

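### Quality of life: the between-arm t-tests use no baseline covariate and follow a baseline test with no stated consequence, while the mixed model's baseline handling, its use of site and the leading analysis are not stated

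*Combined protocol and SAP*

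**What the plan says.** Section 4.2 lists as a secondary objective: "Compare acute and long-term toxicity as well as quality of life for both Endo-HDR and CRT". Section 14.5 gives the analysis in several steps.

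- A preliminary test: "After confirming that there are no baseline differences in quality of life across the two treatment arms using independent samples t-test". No significance level is given for it, and nothing says what follows if a difference is found.
- Pre- to post-treatment changes are computed, and "the difference between these change scores will be evaluated by paired-sample t-tests".
- The arm comparison: "We will compare the quality of life scores at each endpoint as well as the differences between the two arms using two-sample t-test". No covariate is named.
- The threshold: "Given the plurality of comparisons, p-values <0.01 will be considered statistically significant". Sidedness is not stated.
- In addition, "mixed effect models will be used for assessing the quality of life change over time and comparing the two treatment arms". A further sentence says these models serve "to compare the effects of the two treatment arms on change in QOL over time". Whether baseline enters as a covariate, as part of the outcome or not at all is not said.

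Section 6.5 randomises 2:1 "using the method of randomly permuted blocks in strata defined by study site". Section 14.5 does not mention site in the quality-of-life models. No other section specifies baseline adjustment for quality of life, although section 9.1 collects every EORTC questionnaire at baseline.

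**The concern.** The plan offers three ways to compare the arms (raw scores, change scores, mixed model) and does not say which one leads. For the two that are fully described, baseline is either unused (raw) or used only by subtraction (change). Neither is the most precise use of a baseline that every patient is asked to supply, and the control arm has only 46 patients.

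The preliminary test adds nothing to this. A non-significant result leaves any chance imbalance where it was, and a significant one leaves the analyst without an instruction. The second case is not remote: with ten scales tested at 0.05 (number, level and independence are all assumptions), the chance of at least one significant baseline result is 1 − 0.95^10 = 40%.

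At stake is the precision of a stated secondary comparison, and how clearly its result was fixed in advance. The primary pCR comparison is a separate analysis and is untouched.

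**Working it through.** **Inputs from the documents.** 92 Endo-HDR and 46 control patients (section 14.2.1); threshold 0.01 (section 14.5). The plan gives no power, SD, effect size or correlation for quality of life, so there is no figure of its own to reproduce here. The sample size itself does reproduce: a one-sided Fisher exact test at 0.1 with 30% vs 13% and 92 vs 46 gives 80.2% power, against the stated 80%.

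**Assumptions.** Two-sided test; one scale at one visit; normal scores with the same SD (set to 1) at both times; complete data; true effect 0.5 SD; baseline-to-follow-up correlation r = 0.3, 0.5 or 0.7.

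**Step 1, standard error.** For unit variance, SE = √(1/92 + 1/46) = 0.1806.

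**Step 2, variance factor v of each contrast.** Raw score: 1. Change score: 2(1 − r). Baseline-adjusted: 1 − r².

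**Step 3, power.** Noncentral t with noncentrality 0.5/(0.1806 × √v). Critical value 2.61, on 136 df for the t-tests and 135 df with the covariate.

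| r | Analysis | v | Noncentrality | Power | Effect detectable with 80% power |
|---|---|---|---|---|---|
| any | Raw | 1.00 | 2.77 | 0.563 | 0.625 SD |
| 0.3 | Change | 1.40 | 2.34 | 0.396 | 0.739 SD |
| 0.3 | Adjusted | 0.91 | 2.90 | 0.614 | 0.596 SD |
| 0.5 | Change | 1.00 | 2.77 | 0.563 | 0.625 SD |
| 0.5 | Adjusted | 0.75 | 3.20 | 0.720 | 0.541 SD |
| 0.7 | Change | 0.60 | 3.58 | 0.830 | 0.484 SD |
| 0.7 | Adjusted | 0.51 | 3.88 | 0.895 | 0.446 SD |

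To match 138 patients analysed with adjustment, a t-test needs 138 × v/(1 − r²) patients. That is 212/184/162 for change and 152/184/271 for raw at r = 0.3/0.5/0.7. With 5% drop-out (87 vs 44), power is 0.374/0.537/0.807 (change), 0.537 (raw) and 0.587/0.693/0.877 (adjusted), so the ordering is unchanged.

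**Step 4, an imbalance that passes the baseline test.** Suppose the baseline test is run at 0.05 (assumed) and the baseline z is 1.9, which is a difference of 1.9 × 0.1806 = 0.343 SD. With no true effect:

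- The raw contrast is shifted by r × 0.343 = 0.10/0.17/0.24 SD.
- The change contrast is shifted by (r − 1) × 0.343 = −0.24/−0.17/−0.10 SD.
- Given that baseline, the raw z has mean 1.9r and SD √(1 − r²). The change z has mean −1.9√((1 − r)/2) and SD √((1 + r)/2). The chance of exceeding ±2.576 is 1.8%/3.0%/4.0% (raw) and 3.6%/3.0%/2.3% (change).
- With the covariate, the shift is removed and the rate stays at 1%.

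**Step 5, all trials that pass.** Averaging the same probabilities over every baseline z within ±1.96 gives 0.92%/0.76%/0.49% (raw) and 0.65%/0.76%/0.86% (change). All are below the nominal 1%. Over all randomisations, whether or not the test is passed, both t-tests hold 1%.

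**The case against.** The strongest reply is that nothing stated is invalid. Both two-sample t-tests are unbiased under randomisation and hold their level. The change-score test does use baseline, by subtraction. The mixed model may already contain baseline, since a model for change over time most naturally includes it. On that view this is incomplete detail on an unpowered secondary endpoint of a phase II trial. Most of this stands, and it is why the precision loss is conditional on the t-tests carrying the result.

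Four stronger readings are tempting, and the documents do not support them.

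- *Passing the baseline test inflates false positives.* The raised rates in step 4 belong to one imbalance near the edge of a test whose level the plan does not give. Across all trials that pass, the rate is below 1%.
- *The raw and change tests conflict, so one must be wrong.* With the assumed 0.5 SD effect they disagree in about 33%/33%/38% of simulated trials at r = 0.3/0.5/0.7. With no effect the figure is about 1.8%. Two valid tests with moderate power will often differ. That is a reason to name one in advance, not a separate defect.
- *The arms will be compared by paired t-tests.* The wording of that sentence is loose, but section 14.5 assigns the arm comparison to two-sample tests. As a within-arm pre/post test the paired test is sound.
- *A baseline comparison can never be informative here.* That assumes the baseline forms precede allocation. Sections 6.2 and 9 tie baseline only to the six weeks before radiation starts, and section 6.5 lets randomisation come before some baseline procedures. If forms are completed once the arm is known, a baseline difference might not be pure chance.

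The figure of 92 vs 46 is also optimistic for some domains that section 14.5 emphasises. Several QLQ-CR38 sexual items apply to one sex or only to sexually active patients, and items 55 to 61 apply only without a stoma. Section 7.4.4 gives every patient with an anastomosis a diverting ileostomy, so the bowel items will have few respondents until closure.

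**Conclusion.** The point holds as one of precision and specification. If the two-sample t-tests carry the quality-of-life result, baseline adjustment would do better than both at every correlation examined. The variance is 9%/25%/49% lower than for raw scores and 35%/25%/15% lower than for change scores at r = 0.3/0.5/0.7. Neither t-test is reliably the better of the two: change is weaker at low correlation and raw at high. If the mixed model carries the result, the text does not show whether anything is lost.

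The baseline test offers no protection in a given trial and has no stated consequence. A reader might infer that the planned tests are invalid or ignore baseline altogether; neither is so.

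The sizes rest on an assumed 0.5 SD effect, r from 0.3 to 0.7, equal SDs, normal scores, two-sided testing and complete data, none of which the documents supply. The change is recommended because it is nearly free. It does not bear on the pCR conclusion.

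**What to change.** Amend section 14.5 as follows.

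- Name the planned mixed model as the main between-arm analysis, with baseline score as covariate, visit, arm, arm-by-visit and randomisation site. Report the arm contrast with its confidence interval at the existing p<0.01 threshold, and say at which visit and in which of the listed domains the main contrast is taken.
- Use a common baseline mean instead of the covariate only if baseline forms are completed before allocation is known, and state that timing.
- Drop the baseline test as a precondition and report baseline scores descriptively by arm.
- Keep the two-sample t-tests as supportive analyses.
- Reword the paired t-test sentence so that it plainly describes pre- to post-treatment change within each arm.

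The cost is wording. The model is already planned and the baseline questionnaires are already in the survey calendar, so no extra patients, visits or data are needed.
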